**PROTOCOL CHANGES BY VERSION**

Version 5	
 
• Spelling and grammar corrections (throughout document).
 
• Updating project manager contact information.
 
• Update to the estimation of the required sample size (p.22)
 
• Updates to the final sample size number (throughout document).
 
• Clarification of the time windows for completing survey instruments (pp. 16-17)
 

Version 4	
 
• Study coordinator information (pg. 2)
 
• Study Completion Date (pg. 12)
 
• Additional information regarding the re-estimation of the required sample size (pg. 22)
 

Version 3	
 
• Spelling and grammar corrections (throughout document).
 
• Clarification of recruitment goal from 380 to 420. The recruitment goal was increased due to incomplete data from one of the study sites due to research coordinator abruptly leaving the position. (pg 22)
 
• Clarifications about changes made for the COVID pandemic to ensure phone enrollment and that enable the consent process and entire study to be completed virtually (no in-person interaction needed) (pgs 11-12, 21).
 
• Clarification that funder, the Patient-Centered Outcomes Research Institute (PCORI), closely communicates with the study team and is committed to working with the team and extending enrollment dates so as to facilitate meeting study enrollment goals despite both initial delays in enrollment initiation at some study sites and delays related to the ongoing COVID-19 pandemic (pgs 11-12).
 
• Revised references with in-manuscript citations (throughout document).
 
• Updated Table of Contents numbering (pgs 4-5)
 

**PROTOCOL SYNOPSIS**

TITLE	A Multi-Center Randomized Controlled Trial of Perioperative Palliative Care Surrounding Cancer Surgery for Patients and their Family Members
INDICATION	Curative-Intent, Surgery for Upper GI cancer
PRIMARY OBJECTIVE(S)	Patient Quality of Life
SECONDARY OBJECTIVE(S)	Patient: symptom experience, spiritual distress, prognostic awareness, health care utilization, and mortality. Caregiver: quality of life, caregiver burden, spiritual distress, and prognostic awareness.
TREATMENT SUMMARY	Participants randomized to the intervention arm receive five (5) visits with a Palliative Care specialist clinician
SAMPLE SIZE	380 participants

## SCHEMA

## LIST OF ABBREVIATIONS AND DEFINITION OF TERMS

ADL	Activities of daily living
AE	Adverse event
CRF	Case report/Record form
CR	Complete response
DSMC	Data Safety Monitoring Committee
GI	Gastrointestinal
IRB	Institutional Review Board
PC	Palliative Care
PR	Partial response
PRO	Patient-reported outcomes
RECIST	Response evaluation criteria in solid tumors
RR	Response rate
SAE	Serious adverse event

**Of Note: Protocol has been peer-reviewed and published, please see:**

**[name], et. al. “A Multicenter, Randomized Controlled Trial of Perioperative Palliative Care Surrounding Cancer Surgery for Patients and Their Family Members (PERIOP-PC).” Journal of Palliative Medicine. Sep 2019. S-44-S-57. <http://doi.org/10.1089/jpm.2019.0130>. PMID: 31486730**

## 1. OBJECTIVES

### 1.1. Primary Objective

Complete a multi-center, comparative effectiveness, randomized controlled trial comparing the impact of surgeon-palliative care team co-management versus surgeon alone management on multiple patient-reported outcomes (PROs), including patient quality of life at 12 weeks after surgery (primary outcome) (n=380; months 1-36).

### 1.2. Secondary Objectives

Patient: symptom experience, mood symptoms, spiritual distress, prognostic awareness, health care utilization, and mortality. Caregiver: mood symptoms, caregiver burden, spiritual distress, and prognostic awareness.

## 2. BACKGROUND

### 2.1 Study Disease

Despite positive outcomes associated with specialist palliative care in diverse medical oncologic populations, no research has investigated specialist palliative care in surgical oncologic ones.

Moreover, although cancer surgery is predominantly safe, operations can be extensive and with not insignificant potential for perioperative morbidity and/or mortality.

## 2.2 Study Agent/Device/Procedure

N/A

### **For clinicaltrials.gov compliance**

N/A, this study does not involve any drug or biologic treatment, and does not require an Investigational New Drug application (IND).

## 2.3 Rationale

Although cancer surgery is safer than ever before, perioperative morbidity and mortality are not inconsequential and studies suggest that cancer patients and their families suffer significant psychological and physical symptoms surrounding surgery and for weeks to months after surgery. Palliative care is patient- and family-centered care that symptomatically and psychosocially supports seriously ill patients and their families and optimizes quality of life, regardless of diagnosis, prognosis, or care goals. Studies among medical oncology patients support that proactive palliative care: improves quality of life, betters physical and psychological symptom management, betters understanding of prognosis, lessens spiritual distress, lessens caregiver burden, improves caregiver social well-being, decreases caregiver psychological distress, lowers care costs, decreases aggressive end-of-life care interventions, and may even prolong patient survival. Although frequently conflated with hospice, palliative care is for any patient with serious illness and their caregivers; evidence from a randomized controlled trial in patients undergoing curative-intent bone marrow transplantation for treatment of hematologic malignancies supports that proactive palliative care improves patient quality of life, decreases patient physical and psychological symptoms, and decreases caregiver psychological symptoms. Despite these benefits, there have been no studies translating proactive palliative care from a medical oncologic to a surgical oncologic population and none comparing surgeon-palliative care team co-management versus surgeon alone management across patient-reported outcomes (PROs). Indeed, multiple studies even document surgical culture resistance to palliative care involvement, particularly any discussions that might concern end-of-life care.

## 2.4 Study Design

### **For clinicaltrials.gov and Stanford Clinical Trials Directory compliance**

This study is a randomized control trial. The primary purpose of this protocol is Supportive Care, designed to evaluate one or more interventions where the primary intent is to maximize comfort, minimize side effects or mitigate against a decline in the subject's health or function. In general, supportive care interventions are not intended to cure a disease. The interventional model is a Parallel study, in which one of two groups in parallel is exposed to the intervention for the duration of the study. There is only one intervention arm. This study is single blinded, in which the PI and analysts are blinded to randomization. The outcomes of this protocol are designed to evaluate Efficacy.

## **2.5 Correlative Studies Background**

N/A, there are no correlative studies planned.

# **3. PARTICIPANT SELECTION AND ENROLLMENT PROCEDURES**

## **3.1 Inclusion Criteria**

- 3.1.1 Patient is pursuing non-emergent, upper gastrointestinal cancer-related surgery with a goal of primary resection of the tumor – optimal surgical goal is cure, not merely disease palliation.
- 3.1.2 Eligible cancers for this study include pancreatic, hepatocellular, esophageal, gastric, and/or cholangio-carcinomas.
- 3.1.3 Must have no previous involvement of specialist palliative care providers in their care course.
- 3.1.4 Potential study patients must be able to give informed consent and be at least 18 years of age. As assessment for capacity for informed consent is a standard part of the surgical consent process, no patient is referred for the study without having been seen by the surgeon and deemed competent per the surgical team standard protocols.
- 3.1.5 No ECOG or Karnofsky Performance Status will be utilized.
- 3.1.6 One caregiver per patient is also asked to participate. In addition to being identified by the patient as being a key caregiver throughout the surgery period, these caregivers must also be able to give informed consent and be at least 18 years of age.
- 3.1.7 Ability to understand and the willingness to sign a written informed consent document.

## **3.2 Exclusion Criteria**

- 3.2.1 Previous involvement of palliative care providers in patient's care course.
- 3.2.2 Not having one of the eligible cancers: Pancreatic, hepatocellular, esophageal, gastric, or cholangio-carcinoma.
- 3.2.3 Pursuit of emergent surgery for the upper gastrointestinal cancer.
- 3.2.4 No exclusion requirements due to co-morbid disease or incurrent illness.
- 3.2.5 Pregnant or nursing patients will not be excluded from the study.

3.2.6 Patients who are cancer survivors or those who are HIV-positive will be not excluded from the study.

### **3.3 Informed Consent Process**

All participants are provided a consent form describing the study with sufficient information for participants to make an informed decision regarding their participation. Participants either sign the IRB approved informed consent prior to participation in any study specific procedure or, through a waiver due to the COVID-19 pandemic, provide verbal consent with waiver of signature. The participant receives a copy of the consent document. The original signed copy of the consent document or documentation of the verbal consent under the COVID-19 pandemic-related waiver is retained by the research team.

### **3.4 Registration Process**

A trained research coordinator obtains consent. The research coordinator is familiar with all aspects of the study. Consent is obtained either in-person at Stanford Hospital or clinics after the research coordinator approaches potential patients about the study or via telephone after the study has been introduced by the patient's surgical oncologist. As much time as necessary is devoted to consent discussion, with ample time for patients or caregivers to ask any questions. If participants are unsure about their participation, they have the opportunity to contact the study team prior to their surgery. To minimize the possibility of coercion, the research coordinator emphasizes that participation is completely voluntary and that patients or caregivers are not required to participate in the study. During the consenting process, the research coordinator questions the patient or caregiver to verify that they understand the purpose and summary of the study as what would be required of them; if participants do not understand English or have a hearing impairment, we use translators in the consent process.

To register the subject, the study site utilizes the central Stanford study REDcap database. The individual enters all subject eligibility and consent information. No subject begins treatment prior to registration and assignment of a subject identification number.

At registration, each study site coordinator assigns eligible subject an identification number. This identification number is used on the shared Stanford REDcap database as the record indicator. The subject's identification number is used on all subject-specific Case Report Forms (CRFs) and serious adverse event (SAE) forms. Participant information is entered into Oncore within 7 days.

### **3.5 Randomization Procedures**

Randomization is immediately after enrollment, stratified by study site, and completed via computer-generated random allocation with a block size of 6 by using the REDcap database. Understandably, neither the patient, caregiver, nor surgeon can be blinded to intervention allocation. However, the principal investigator (PI) and analysis team are blinded to participant randomization and the research team acquiring outcome data, whenever possible, is blinded to participant randomization.

### 3.6 Study Timeline

#### Primary Completion:

The study was scheduled to reach primary completion 24 months from the time the study opens to accrual. Initial delay in enrollment at some of the study sites and the ongoing COVID pandemic have led to enrollment delays. Yet, the study team communicates closely with the funder (the Patient-Centered Outcomes Research Institute; PCORI); PCORI is committed to this study and its success and willing to support a longer study duration, if that is needed to enable full study enrollment.

#### Study Completion:

The study was to reach completion approximately 24 months from the time the study opened for accrual. Yet, as previously mentioned, that accrual has been delayed due to study site delays in starting enrollment and the ongoing COVID-19 pandemic. Yet, the study team and PCORI communicate closely and PCORI is supportive of continuing the trial as needed to ensure meeting enrollment goals. Based on the most recent call with our program officer (June 23, 2021), our current tentative end date is December 31, 2022.

Study start date: March 2019.

Anticipated study completion date: December 2022

## 4. TREATMENT PLAN

This is a multi-center, comparative effectiveness randomized controlled trial comparing the impact of surgeon-palliative care team co-management versus surgeon alone management on PROs, including quality of life (primary outcome), symptom score, caregiver burden and spiritual distress. The two study arms are below:

- 1) Surgeon alone management (Enhanced control) – considered “enhanced usual care” this involves surgeon and surgical team management of symptoms, psychosocial support, and prognostic-related communication. The surgeon and surgical team care for the patient and their family both prior to and following surgery. As consistent with standard practice, the surgeon may consult the palliative care team at any time, if desired. Per PCORI’s request, this study arm is “enhanced” in that surgical oncologists are provided and encouraged to consider following National Comprehensive Cancer Network guidelines as to when to consider formal palliative care consultation.
- 2) Surgeon palliative care team co management (Intervention) – All patients receive the care described in the “Surgeon alone management” arm. In addition to this, palliative care is provided by a specialist team and in a way consistent with the palliative care team co-management evaluated in clinical trials of specialist palliative care team co-management for medical oncologic populations. For patients in this arm, patients and/or family members are seen by the palliative care team: (1) prior to surgery, (2) during their hospitalization for their surgery, and (3) on an at least monthly basis until 12 weeks following surgery. Consistent with previous palliative care interventions, post-operative palliative care interactions following patient discharge from the hospital can be in person at the outpatient clinic, via a telehealth visit, or via telephone, Facetime, or Skype, whichever is preferred by the patient and family.

#### **4.1 General Concomitant Medication and Supportive Care Guidelines**

N/A, there is no use of concomitant medications or additional appropriate supportive care medications or treatments. Any palliative care-related medication changes for patients in the intervention arm are determined through discussion between the palliative care specialist and surgical teams.

#### **4.2 Criteria for Removal from Study**

Participants could be removed from study at any time if they choose to withdraw, or if the surgeon chooses to withdraw the patient from the study.

#### **4.3 Alternatives**

N/A, this has been deemed a low-risk study; the only potential risk to participants is considered to be breach of confidentiality.

### **5. INVESTIGATIONAL AGENT/DEVICE/PROCEDURE INFORMATION**

#### **5.1 Investigational Agent/Device/Procedure**

N/A

#### **For clinicaltrials.gov and Stanford Clinical Trials Directory compliance**

N/A

#### **5.2 Availability**

N/A

#### **5.3 Agent Ordering**

N/A

#### **5.4 Agent Accountability**

N/A

### **6. DOSE MODIFICATIONS**

N/A

### **7. ADVERSE EVENTS AND REPORTING PROCEDURES**

#### **7.1 Potential Adverse Events**

We do not anticipate adverse events related to the study, as this is a low-risk complex behavioral study. No investigational agents or procedures are being studied.

## 7.2 Adverse Event Reporting

Adverse Events will be clearly noted in source documentation and listed on study specific Case Report Forms (CRFs). The Protocol Director (PD) or designee will assess each Adverse Event (AE) to determine whether it is unexpected according to the Informed Consent, Protocol Document, or Investigator's Brochure, and related to the investigation.

### ***Regulatory and reporting requirements***

It is the responsibility of the investigator to document all adverse events which occur during the investigation. Anticipated day-to-day fluctuations of the disease under study that do not represent a clinically significant exacerbation or worsening need not be considered an adverse event.

### ***Reporting Serious Adverse Events***

N/A there are no investigational agents being studied.

Any SAEs which occur as a result of protocol specific diagnostic procedures or interventions must be reported to the local DSMC and local IRB (using the formed attached or an allowable local form) and to the coordinating site (Stanford University).

## 8. CORRELATIVE/SPECIAL STUDIES

N/A There are no correlative studies planned in relation to this randomized clinical trial.

## 9. STUDY CALENDAR

	Pre-Study	1 Week Before Surgery	1 Week After Surgery	1 Month After Surgery	2 Months After Surgery	3 Months After Surgery	4 Months After Surgery	5 Months After Surgery	6 Months After Surgery	Off Study d
Palliative Care Visit		X	X	X	X	X				
Informed consent	X									
Demographics	X									
Medical Abstraction										X
FACIT-PaL		X	X	X		X			X	
ESAS		X	X	X		X			X	
FACIT-Sp-12		X	X	X		X			X	
PROMIS-29		X	X	X		X			X	
Presence of Advance Care Planning	X								X	
(Caregivers) ZBI-12, PROMIS 29, FACIT-Sp-12		X	X	X		X			X	
Adverse event evaluation		X.....							X	X
Other tests, as appropriate										
Other correlative studies										

## 10. MEASUREMENTS

### For clinicaltrials.gov and Stanford Clinical Trials Directory compliance

**Note: Each outcome measure listed within the protocol will necessitate legally required results reporting to clinicaltrials.gov within one year after the completion of the primary outcome measure.**

#### 10.1 Primary and Secondary Outcome measures

The primary outcome variable of this project is patient-reported quality of life.

##### 10.1.1 Relevant Subset

All participants will be assessed for primary outcome.

##### 10.1.2 Measurement Definition

The primary outcome variable of this project is patient quality of life, measured by the Functional Assessment of Chronic Illness Therapy—Palliative Care (FACIT-PaL) Subscale.

	Study design	Participants	Outcomes and Measurement Times
SA1 (months 1-36)	
Randomized controlled trial (n=420 patients; Approx. n = 304 family members); Outcomes measured at approximately: - enrollment - 1 week after surgery - 1 month after surgery - 3 months after surgery - 6 months after surgery
	
Patients
 
Family members/ Companions
	
(1) Quality of life - Functional Assessment of Chronic Illness – Palliative Care (FACIT-PaL)** Subscales: (i) Functional Assessment of Cancer Therapy (FACT-G) (ii) Trial Outcome Index (TOI)
 
(2) Demographics
 
(3) Edmonton Symptom Assessment Score (ESAS)*
 
(4) Functional Assessment of Chronic Illness Therapy – Spiritual Well-being (FACIT-Sp-12)*
 
(5) Mood symptoms including anxiety and depression subscales – PROMIS-29
 
(6) Health care utilization* (# of post-operative hospitalizations and/or emergency room visits)
 
(7) Presence of advance care planning*
 
(8) Prognostic understanding*
 
(9) Mortality*
 
(1) Demographics
 
(2) Zarit Caregiver Burden Scale (ZBI-12)*
 
(3) Mood symptoms including anxiety and depression subscales – PROMIS-29
 
(4) Functional Assessment of Chronic Illness Therapy – Spiritual Well-being (FACIT-Sp-12) family/companion measure*
 
(5) Prognostic understanding*

### 10.1.3 Measurement Methods

The primary outcome variable of this project is patient quality of life, measured by the Functional Assessment of Chronic Illness Therapy—Palliative Care (FACIT-PaL) Subscale. This subscale has not been previously used in a surgical population; however, FACIT-PaL includes all of the elements of Functional Assessment of Cancer Therapy-General (FACT-G), which have been used extensively as a quality-of-life outcome in cancer populations.

### 10.1.4 Measurement Time Points

The outcome of quality of life will be assessed at baseline during enrollment, one week after surgery, one month after surgery, 3 months after surgery, and 6 months after surgery. Participants will have a window of +/- 7 days to complete the surveys for each timepoint before it is considered “missed.”

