## 12.1 Statistical Design

Differences in primary and secondary outcomes between intervention and control arms will be evaluated at each individual time point as well as across the intervention period.

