## 12.4 Primary Analysis

The primary outcome for this study is quality of life three months following surgery.

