### 12.4.2. Analysis Plan

The effect of group assignment (intervention or control) on the quality of life will be tested. Differences in outcomes between two arms at each visit will be tested by the two-sample t-test/Mann-Whitney test or Fisher's exact test/chi-squared test based on the data types of the outcomes. The effect of intervention on the quality of life after accounting for various confounding variable will be determined using a linear mixed model that accounts for within-subject variations due to repeated measures. Sensitivity analyses will assess whether there are differential effects on contingent on patient or study site characteristics on the primary outcomes.

The overall level of statistical significance was set at  $p<0.05$ . For all models, the research team will identify possible confounding variables for model adjustment, including baseline attributes. Using peer-reviewed literature, the research team has identified confounding variables that models will be adjusted for. These covariates include patient gender, age, race, education, and health status.

Qualitative data related to secondary outcomes will be transcribed, de-identified, and analyzed

based on qualitative description. A HIPPA-compatible, professional transcription service will be used for interview transcription. NVivo software will be used for qualitative analyses. A codebook will be determined by a three-person team with a single coder then analyzing the transcripts. Line-by-line, axial, and theoretical consensus coding will be used to organize and summarize findings, which will be validated through triangulation, member checking, and search for disconfirming data.

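### The uniform ±7-day survey window lets forms from the day of surgery through day 14 count as the 1-week assessment, which blurs that comparison

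*Combined protocol and SAP*

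**What the plan says.** Section 10.1.4 has quality of life "assessed at baseline during enrollment, one week after surgery, one month after surgery, 3 months after surgery, and 6 months after surgery". It then gives one rule for all of these: "Participants will have a window of +/- 7 days to complete the surveys for each timepoint", after which a form counts as missed. Section 10.2.4 repeats the rule for the secondary outcomes. No section gives the 1-week visit a narrower or one-sided window, excludes the day of surgery, or sets an order between the form and the in-hospital palliative care contact.

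In the intervention arm, Section 4 places that contact "2) during their hospitalization for their surgery", with no day given. The Section 9 calendar marks "Palliative Care Visit" in the column for one week after surgery. The same column holds FACIT-PaL, ESAS, FACIT-Sp-12, PROMIS-29 and the caregiver forms.

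The 1-week data are used in planned analyses. Section 12.1 says that differences between arms "will be evaluated at each individual time point as well as across the intervention period". Section 12.4.2 says "Differences in outcomes between two arms at each visit will be tested", and Section 12.5.2 does the same for secondary outcomes. Both sections also fit a "linear mixed model that accounts for within-subject variations due to repeated measures", without saying whether time is the nominal visit or the actual day. Section 12.4 fixes the primary timepoint: "The primary outcome for this study is quality of life three months following surgery".

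**The concern.** A tolerance that is harmless at 3 or 6 months reaches back to the operation itself when the target is one week. A form from day 0 or day 1 and a form from day 14 both count as the 1-week FACIT-PaL, ESAS, PROMIS-29 or FACIT-Sp-12. If scores move quickly in the first two weeks, as one would expect but as the documents do not quantify, these forms describe different stages of recovery. Some intervention patients could also complete the form before their in-hospital palliative contact and others after it.

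What is at stake is the interpretation and precision of the 1-week comparison, for patients and caregivers. The 1-week data also enter the repeated-measures model under a time coding that the plan leaves open.

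**Working it through.** **Inputs.** Window of ±7 days (Sections 10.1.4 and 10.2.4). Targets of 1 week, 1 month, 3 months and 6 months after surgery (same sections). Planned effect of 0.4 SD at 12 weeks, 90% power, two-sided 0.05, 86% completion, 20% variance inflation, 186 per arm (Sections 12.6.2 and 12.6.3). The documents do not convert months to days; I take 28 to 30 days, 84 to 91 days and 182 days.

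**The plan's own sample size.** The normal formula gives 2 × ((1.960 + 1.282)/0.4)² = 131.3 per arm. The t-distribution gives 132.3, rounded up to 133. Then 133 × 1.20 / 0.86 = 185.6, or 186, as stated. The survey window plays no part in this figure.

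**The windows (target ± 7).**

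| Visit | Target day | Valid days | 7 / target |
|---|---|---|---|
| 1 week | 7 | 0 to 14 | 100% |
| 1 month | 28 to 30 | 21–35 or 23–37 | 25% to 23% |
| 3 months | 84 to 91 | 77–91 or 84–98 | 8% |
| 6 months | 182 | 175–189 | 4% |

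Only the 1-week window touches the day of surgery. In addition, if the first survey falls one week before surgery, as in the Section 9 calendar, its window is day −14 to day 0 and meets the 1-week window on day 0. Section 10.1.4 instead places that survey at enrollment, and the two should be reconciled.

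**Noise (assumed inputs).** Suppose scores move 0.05 to 0.1 SD per day in the first two weeks. If completion were spread evenly over days 0 to 14, an unfavourable assumption, the variance of completion day would be 14²/12 = 16.3. The added outcome variance is 16.3 × 0.05² = 0.04 to 16.3 × 0.1² = 0.16 of the outcome variance, that is 4% to 16%. If most forms cluster near day 7, it is smaller.

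**Bias (assumed inputs).** Spurious difference = (arm difference in mean completion day) × (daily slope).

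- If 5% of one arm's forms come 5 days early (day 2 instead of day 7) and none do in the other arm: 0.05 × 5 = 0.25 day. Times 0.05 to 0.1 SD per day, this is about 0.01 to 0.025 SD.
- A 2-day difference would give 2 × 0.05 to 0.1 = 0.1 to 0.2 SD. Reaching it this way needs 2/5 = 40% of one arm's forms to be that early and none in the other.
- If completion day is the same in both arms, the shift is zero whatever the slope.

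**The case against.** The strongest reply is that the window is identical in both arms, the affected visit is not the primary one, and the table in Section 10.1.2 describes the measurement times as approximate. All of that stands, and it limits the point to the 1-week visit.

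A reader might infer more in four ways.

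- **That the 1-week comparison is biased.** Bias needs completion day to differ by arm, and no section shows or implies that it does. Outcome data are collected by the research team, blinded where possible (Sections 3.5 and 12.1.1), not by palliative clinicians. Surgeons of control patients may also request a palliative consultation (Section 4), so palliative contact is not exclusive to one arm.
- **That early forms precede all intervention.** They may precede the in-hospital contact, but intervention patients are also due to be seen before surgery (Sections 4 and 9).
- **That a form filled in before the operation is valid.** The timepoint is defined as after surgery, so that reading is strained. A form later on day 0, or on day 1, is allowed. The documents do not say how often this happens, and it is probably rare.
- **That early forms should be dropped from the main comparison.** Sections 12.4.1 and 12.5.1 commit to using all data regardless of adherence, and completion day arises after randomization, so excluding on it could itself unbalance the arms.

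What remains is that the rule as written admits these forms, nothing else narrows it, and the visit is formally tested.

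**Conclusion.** The point holds as a weakness in how the 1-week visit is defined. That the window runs from day 0 to day 14 follows directly from the text. The likely consequence is extra variability and a 1-week result that is hard to interpret. Under the assumed slopes and an even spread of completion days, the variance rises by 4% to 16%, and by less if completion clusters near day 7. Bias is possible but not shown; with 5% of one arm's forms five days early it would be about 0.01 to 0.025 SD.

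The documents do not support saying that the primary result is compromised. At 3 months the tolerance is about 8% of the elapsed time, and the 186 per arm does not depend on it. Nor is it shown that the 1-week data distort the 3-month contrast through the mixed model; the plan simply does not say how time is coded there.

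**What to change.** **Remaining 1-week assessments.** In Sections 10.1.4 and 10.2.4, give this visit its own window with a lower bound clearly after surgery (day 4 or day 5, for example, to be chosen by the investigators) and day 14 as the upper bound. Keep ±7 days for later visits. Section 12.6.1 reports 381 enrolled by March 31, 2022 against the goal of 380, so this may reach few patients and the analysis rules below matter more.

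**Forms already collected.** Before unblinding, add to Sections 12.4.2 and 12.5.2:

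- All forms stay in the intent-to-treat analysis.
- The linear mixed model uses actual days since surgery as its time variable, with the shape of the time trend specified, or this is a pre-specified sensitivity analysis.
- The 1-week completion day is summarized by arm.
- The 1-week comparison is repeated without very early forms as a sensitivity analysis only, with the cut-off fixed in advance.

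**Cost.** One sentence in each of two sections, a short addition to the analysis plan, slightly more analysis work, and possibly a few more missed 1-week forms. The analysis part depends on completion dates having been recorded. The documents describe the REDCap database but do not say that it holds survey dates, so the sponsor should confirm this first.
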